12 ETHICS AND RESPONSIBILITIES

12.1 Good Clinical Practice

The study will be performed in accordance with the ethical principles in the Declaration of Helsinki, Good Clinical Practices (GCPs) and applicable regulatory requirements.

12.2 Institutional Review Board/Independent Ethics Committee

The final study protocol, including the final version of the Subject Information and Consent Forms, must be approved in writing by an IRB that meets the minimum FDA standards before enrollment of any subject into the study. The PI or their designee is responsible for informing the IRB of any SAE and amendment(s) to the protocol as per regulatory requirements.

12.3 Informed Consent

The Investigator will ensure that the subject or a legally authorized representative of the subject is given full and adequate oral and written information about the nature, purpose, possible risk and benefit of the study. Subjects must also be notified that they are free to discontinue from the study at any time. The subject should be given the opportunity to ask questions and allowed time to consider the information provided. ***The subject's signed and dated informed consent must be obtained before conducting any study specific procedure.*** The consent form that is used must meet the requirements as outlined in the ICH Guidance on GCPs (E6) and must be approved by both the reviewing IRB and by Soligenix.

12.4 Subject data protection

The Subject Information and Consent Form will explain that study data will be stored in a computer database, maintaining confidentiality. Subjects in this database will be identified by initials or enrollment code/subject number only. Authorized representatives of a regulatory authority (eg, FDA) may require direct access to parts of the trial site records relevant to the study, including subjects' medical history for data verification purposes.

12.5 Financial Disclosure

The FDA has issued regulations (21 CFR Part 54) that require Sponsors (in this case Soligenix) to submit complete and accurate certification or disclosure statements to certify the absence of certain financial interests of clinical investigators and/or disclose those financial interests, as required, when clinical studies are submitted to the FDA in support of marketing approval of a new drug application (NDA). These regulations are intended to ensure that financial interests and arrangements of clinical investigators, that

could affect reliability of data submitted to the FDA in support of marketing approval, are identified and disclosed by the Sponsor.

Clinical investigators shall be asked to disclose proprietary (eg, patent, licensing agreement) and financial (eg, stock options, royalty) interests as they pertain to Soligenix, prior to participating in the study. In addition, clinical investigators will be required to consult with Soligenix before acquiring any financial interest in the company and must disclose any change in their proprietary or financial interests if it occurs during the course of the study and for one year following study completion. Clinical Investigator is defined under Title 21 CFR Part 54 as an investigator or sub-investigator listed on the FDA Form 1572 that is directly involved in the treatment or evaluation of research subjects. The requirement for proprietary and financial disclosure also includes any ownership by the spouse or any dependent child of the investigator.

If the FDA determines that the financial interests of any clinical investigator raise serious questions about the integrity of the data, the FDA will take any action it deems necessary to ensure the reliability of the data, including:

- Initiating agency audits of the data derived from the clinical investigator in question;
- Requesting that the Sponsor submit further analyses of data, eg, to evaluate the effect of the clinical investigator's data on overall study outcome;
- Requesting that the applicant conduct additional independent studies to confirm the results of the questioned study; and/or
- Refusing to treat the covered clinical study as providing data that can be the basis for an agency action.

If the Sponsor does not include certification or disclosure, or both, if required, or does not certify that it was not possible to obtain the information, the FDA may refuse to file the NDA.

13 RECORDS MANAGEMENT

13.1 Source Documentation

Original source documents include all informed consent forms, laboratory reports, progress notes, medical histories, physical and diagnostic findings, diagnoses and dates of therapy prior to and during this study, drug dispensing/disposition records which are used to support the data recorded CRFs of each subject. When possible, all data should be documented in an original source document and copied into the CRF.

13.2 Study Files and Record Retention

Copies of CRFs should be retained by sites along with all original source documents (eg, informed consent forms, laboratory reports, progress notes, medical histories, physical and diagnostic findings, diagnoses and dates of therapy prior to and during this study, drug dispensing/disposition records) that support CRFs of each subject must be retained in the files of the responsible investigator or in hospital records for a minimum of two (2) years following notification by Soligenix that all investigations have been discontinued or that the last approval of a marketing application has been obtained.

If the responsible investigator retires, relocates, or for other reason withdraws from the responsibility of keeping the study records, custody must be transferred to a person who will accept the responsibility. Soligenix must be notified in writing of the name and address of the new custodian.

14 AUDITING AND MONITORING

14.1 Study Monitoring

It is the responsibility of the PI and site personnel to assure that the data recorded in the CRF is accurate, complete and can be verified from the medical records.

In accordance with the Guidelines for the Monitoring of Clinical Investigations presented in the ICH Guidance on GCPs (E6), Soligenix will select, either directly or through subcontract, qualified individuals to monitor the progress of the study and adherence to protocol by the individual clinical sites.

It is the responsibility of the PI to assure that, at mutually agreed upon times, the clinical monitor has appropriate access to all medical records, study materials, study and regulatory binders, laboratory and radiographic results, study personnel, their time to allow adequate assessment as to the quality, completeness and adherence to all aspects of the protocol.

14.1.1 *Pre-study Evaluation*

This initial encounter with the site will establish that the site has all of the necessary elements to successfully participate in the proposed protocol including adequately trained staff, adequate free time of the staff, adequate facilities for safe and proper trial conduct, evidence for potential enrollment of suitable patients, adequate research pharmacy support, the presence of an IRB meeting the local and FDA requirements, and a commitment for training of all involved staff on the protocol.

14.1.2 *Site Initiation Visit*

Once all required trials documents have been processed, the Medical Monitor (or trained designee) will initiate the study after on-site training of the participating staff at the institution. Topics covered will include training on:

- The investigational status of the study drug and the requirements for its accountability.
- Background on the study drug.
- Details of the protocol including patient selection, study drug administration, procedures to be performed, and visit schedules.
- Critical nature of obtaining informed consent in accordance with the Declaration of Helsinki and ICH Guidance on GCPs (E6) before enrolling each subject in the study.
- The obligation to ensure IRB review and approval for the study, including the protocol, amendments, ICF and any advertisements, is obtained prior to its initiation at his/her clinical site, to ensure continuing review of the study by

the IRB, and to keep Soligenix informed of such approval and subsequent actions concerning the study.

14.1.3 Monitoring Visits

Soligenix or their trained designee will perform on-site monitoring visits as frequently as it deems necessary. At these visits, the site monitor will compare the data entered into the CRFs with the source documents and check for protocol compliance including a record of informed consent, enrollment criteria, all subject assessments, all AEs and all concomitant medications. In addition, study drug and supporting records will be reviewed. Additionally, they assure that all serious, life-threatening or fatal AEs are being reported immediately [and in no case later than twenty-four (24) hours after the event] to the Medical Monitor or designee at Soligenix.

Findings from these reviews will be discussed with the investigator and staff. Completed pages of the CRFs will be evaluated at each visit. The dates of the monitoring visits will be recorded in a sign-in log that will be kept at the site. The study coordinator and investigator are expected to be available for questions, the source documentation readily available, and a suitable environment provided for review of study-related documents.

14.1.4 Close-out Visit

The clinical research monitor(s) will perform an end of trial visit to ensure that:

- All drug reconciliation forms are accurate and complete.
- All unused study drug is returned to the appropriate location.
- All data issues are resolved and CRFs are completed and verified.
- The IRB has been notified that the study has been completed.
- The investigator at each site is aware that the study has been completed and no further subjects are enrolled.

14.2 Audits and Inspections

Health Authorities (eg, FDA), in the person of a trained and properly authorized employee, may request access to all study records, including source documents, for inspection and copying. The investigator will immediately notify Soligenix of any upcoming inspections.

Periodic auditing inspections may also be conducted by a representative of the Quality Assurance Department of Soligenix or its designee(s).

15 AMENDMENTS

Protocol modifications, except those intended to reduce immediate risk to study subjects, may be made only by Soligenix. A protocol change intended to eliminate an apparent immediate hazard to subjects may be implemented immediately, provided the IRB/IEC is notified within 5 days.

Any permanent change to the protocol must be handled as a protocol amendment. The written amendment must be submitted to the IRB/IEC and the investigator must await approval before implementing the changes. Soligenix will submit protocol amendments to the appropriate regulatory authorities for approval.

If in the judgment of the IRB/IEC, the investigator, and/or Soligenix, the amendment to the protocol substantially changes the study design and/or increases the potential risk to the subject and/or has an impact on the subject's involvement as a study participant, the currently approved written informed consent form will require similar modification. In such cases, informed consent will be renewed for subjects enrolled in the study before continued participation.

16 STUDY REPORT AND PUBLICATIONS

Soligenix is responsible for preparing and providing the appropriate regulatory authorities with clinical study reports according to the applicable regulatory requirements.

Soligenix's publication policy is discussed in the investigator's Clinical Research Agreement.

17 STUDY DISCONTINUATION

Both Soligenix and the Principal Investigator reserve the right to terminate the study at the investigator's site at any time. Should this be necessary, Soligenix or a specified designee will inform the appropriate regulatory authorities of the termination of the study and the reasons for its termination, and the Principal Investigator will inform the IRB/IEC of the same. In terminating the study, Soligenix and the Principal Investigator will assure that adequate consideration is given to the protection of the subjects' interests.

18 CONFIDENTIALITY

All information generated in this study is considered highly confidential and must not be disclosed to any person or entity not directly involved with the study unless prior written consent is gained from Soligenix. However, authorized regulatory officials, IRB/IEC personnel, Soligenix and its authorized representatives are allowed full access to the records.

Identification of subjects and CRFs shall be by initials, screening and treatment numbers only. If required, the subject's full name may be made known to an authorized regulatory agency or other authorized official.

20.2 APPENDIX II – SCORD Calculation Worksheet

The following form will be used to calculate a severity of dermatitis score for treated lesions.

SCORING DERMATITIS (SCORD) SCALE

A. Percentage of lesions with dermatitis score (enter % of involved treated lesions)

Score	%
-------	---

Range 0 = no dermatitis in treated lesions to 100 = all treated lesions are entirely involved with dermatitis

A score can range from 0 to 100

B. Lesion severity score (circle average score of affected lesions for each finding)

- a. Redness 0- None 1- Mild 2- Moderate 3- Severe
- b. Oozing/crusting 0- None 1- Mild 2- Moderate 3- Severe
- c. Scratch marks 0- None 1- Mild 2- Moderate 3- Severe
- d. Skin thickening 0- None 1- Mild 2- Moderate 3- Severe
- e. Dryness 0- None 1- Mild 2- Moderate 3- Severe

B score is the sum of the 5 sub-scores and can range from 0 to 18

C. Patient self-reported current itch measured on a 0 to 10 scale marking itch intensity on a visual analog scale. The scale will be 10 cm long and the score is the centimeter from 0 to the patient's slash.

No itch

Worst imaginable itch

8

10

C score is the number of centimeters from 0 and can range from 0 to 10

[figure not shown]
Total SCORD score is calculated by adding the score for each of the subscores (A, B, and C) weighted as follows:

Calculation of SCORD score = (A/5 +7B/2 +C)

20.3 APPENDIX III – Body Lesion Diagram

BODY LESION DIAGRAM

Please identify the index lesions' location (Ex. 1, 2 or 3) in the diagram below.

20.4 Appendix IV - Skin Adverse Event Questionnaire

Patient Number: _____

Date: ____ / ____ / 202 ____

Over the last 24 hours, please rate the degree of discomfort you have had at areas that have been treated with your drug. Place a vertical mark on each line corresponding to the worst area that has been treated for each of the symptoms you have had.

1. Rash:

None | _____ | Worst imaginable

2. Tenderness

None | _____ | Worst imaginable

3. Pain

None | _____ | Worst imaginable

4. Burning

None | _____ | Worst imaginable

5. Swelling

None | _____ | Worst imaginable

6. Redness

None | _____ | Worst imaginable

7. Blistering

None | _____ | Worst imaginable

8. Change in color

None | _____ | Worst imaginable

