6.2.2 Baseline

At the Baseline visit, the following will be done prior to randomization:

- Confirmation that the patient meets all inclusion/exclusion criteria
- History of any medical changes obtained
- Women of child-bearing potential will have a serum pregnancy test obtained unless the screening test was obtained 7 days or less
- Physical exam
- Vital signs obtained
- Blood for the hematology panel obtained
- Blood for the clinical chemistry panel obtained
- Three to five lesions that are representative of the patient's disease and are discrete with defined borders, will be chosen as the index lesions, and classified as patch or plaque lesions
- Charting of all CTCL lesions on the "Body Lesion Diagram" ([APPENDIX III – Body Lesion Diagram](#)) locating and numbering each of the index lesions
- Each index lesion will have an mCAILS score assessed and recorded
- The mSWAT score will be assessed and recorded
- The SAEQ score will be collected and recorded
- The SCORD score will be collected and recorded

Once all of these assessments are completed, the patient will be randomized into one of the two treatment arms, to receive HyBryte or Valchlor as the study drug. Patients who are randomized into the HyBryte treatment arm will follow the assessments outlined in Section [6.2.3](#). Patients who are randomized into the Valchlor treatment arm will follow the assessments outlined in Section [6.2.4](#).

6.2.3 *HyBryte Patients*

Patients who are randomized into the HyBryte treatment arm will be given a jar of ointment at the Baseline visit. They will be instructed on proper drug application and demonstrate proficiency in drug application and all accessible lesions will be treated with study drug.

6.2.3.1 *Standard light treatment clinic visits*

Patients randomized to HyBryte will have HyBryte applied twice weekly and an opaque covering applied for 21 (± 3) hours followed by the administration of visible light encompassing wavelengths of 500 to 650 nm. The light will be administered with a precisely calibrated device with a light dose starting at 6 J/cm² twice weekly that is titrated up according to the physician's discretion on subsequent sessions. Treatment will target a post-light treatment Erythema score of 1. The light dose will be reduced, maintained or treatment administrations may be suspended if a Grade 2 or greater erythema is present. Additional assessments of treated lesions and surrounding areas will include:

- Erythema
- Pain
- Pruritus

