6.2.3.2.1 Light Treatment Day

The patient will return to the clinic 21 (± 3) hours after study drug is applied and the following assessments will be conducted prior to light treatment:

- Each index lesion will have an mCAILS score assessed and recorded
- The mSWAT score will be assessed and recorded
- The PGA score will be assessed and recorded
- The SAEQ score will be collected and recorded
- The SCORD score will be collected and recorded

Once the assessments are completed, the standard light treatment procedures will be conducted, as follows:

- Interval medical history obtained
- Any AEs documented
- Adequate application of the drug will be verified by a pink staining on visual inspection of lesions
- Delivery of light session, the time of treatment calculated by the target dose
- A dermatologic assessment of treated lesions will be performed immediately before and 10 to 30 minutes following completion of the light session. This includes assessment of treated lesions and surrounding areas for:
 - Erythema

- Pain
- Pruritus
- Edema
- Hyperpigmentation
- Hypopigmentation
- Rash
- Vesication

6.2.3.3 Week 12 Session 24

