6.2.3.4 Follow-Up Visits (Week 13, 14, and 16)

Patients will return to the clinic during Weeks 13, 14, and 16 (End of Study) for follow-up assessment. At each follow-up visit, the following will be conducted:

- Interval medical history obtained
- Any AEs documented
- Each index lesion will have an mCAILS score assessed and recorded
- The mSWAT score will be assessed and recorded
- The PGA score will be assessed and recorded
- The SAEQ score will be collected and recorded
- The SCORD score will be collected and recorded
- Vital signs obtained

In addition to the assessments above, the following will be done at the Week 16 Follow-Up/End of Study visit:

- Physical Exam
- Vital Signs obtained
- Blood for the hematology panel obtained
- Blood for the clinical chemistry panel obtained

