6.2.4 Valchlor Patients

Patients who are randomized into the Valchlor treatment arm will be given a tube of gel at the Baseline visit. They will be instructed on proper drug application according to the instructions on the package insert.

6.2.4.1 Week 3, Week 6, and Week 9

Patients will be instructed to come to the clinic during Weeks 3, 6, and 9.

At the clinic, the following assessments will take place before Valchlor is applied:

- Interval medical history obtained
- Any AEs documented
- Each index lesion will have an mCAILS score assessed and recorded
- The mSWAT score will be assessed and recorded
- The PGA score will be assessed and recorded
- The SAEQ score will be collected and recorded
- The SCORD score will be collected and recorded
- Vital signs obtained

Once these assessments have been completed, the patient will apply study drug at the clinic.

6.2.4.2 Week 12

Patients will come in to the clinic at Week 12, and the following assessments and procedures will be completed before Valchlor is applied:

- Interval medical history obtained
- Any AEs documented
- Each index lesion will have an mCAILS score assessed and recorded
- The mSWAT score will be assessed and recorded
- The PGA score will be assessed and recorded
- The SAEQ score will be collected and recorded
- The SCORD score will be collected and recorded
- Physical Exam
- Vital Signs obtained
- Blood for the hematology panel obtained
- Blood for the clinical chemistry panel obtained

Once these assessments and procedures have been completed, the patient will apply study drug at the clinic.

6.2.4.3 *Follow-Up Visits (Week 13, 14, and 16)*

Patients will return to the clinic during Weeks 13, 14, and 16 (End of Study) for follow-up assessment. At each follow-up visit, the following will be conducted:

- Interval medical history obtained
- Any AEs documented
- Each index lesion will have an mCAILS score assessed and recorded
- The mSWAT score will be assessed and recorded
- The PGA score will be assessed and recorded
- The SAEQ score will be collected and recorded
- The SCORD score will be collected and recorded
- Vital signs obtained

In addition to the assessments above, the following will be done at the Week 16 Follow-Up/End of Study visit:

- Physical Exam
- Vital Signs obtained
- Blood for the hematology panel obtained
- Blood for the clinical chemistry panel obtained

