9.1 Definitions

9.1.1 **Adverse Experience (AE)**

Any noxious or unintended event that occurs in association with the use of an investigational agent in humans, *whether considered related to the investigational agent or not*. This definition encompasses symptoms or signs reported by the subject or detected by the Investigator or other competent observer, as well as medically important deviations from normality in the results of ancillary investigations. If present at time of first dose of study drug, such AEs must be recorded as part of the medical history.

9.1.2 **Treatment-Emergent AE**

An AE that is new in onset or aggravated in severity or frequency following entry into the study. In addition, any pathological finding on physical examination or diagnostic procedure that is new in occurrence or exacerbated in comparison with the subject's status at study entry is considered a treatment-emergent AE if it requires any medical or surgical intervention whatsoever (including, but not limited to, additional diagnostic procedures or alteration of prescribed therapy).

9.1.3 **Potentially Serious Adverse Experience**

Any AE that is sufficiently severe or alarming as to require any form of significant medical intervention. Note: Important medical events that may not result in death, be life threatening, or require hospitalization may be considered an SAE when, based upon appropriate medical judgment, they may jeopardize the subject and require medical or surgical intervention to prevent one of the outcomes listed in the SAE definition.

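### At Weeks 3, 6, 9 and 12 the HyBryte text fixes the SAEQ skin checklist before adverse events are documented, while the Valchlor lists put adverse events ahead of the SAEQ without fixing an order; the two arms should follow one sequence.

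*Combined protocol and SAP*

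**What the plan says.** **The questionnaire.** The SAEQ covers rash, tenderness, pain, burning, swelling, redness, blistering and change in color over the previous 24 hours (7.2.3, Appendix IV). For each symptom the patient marks a line for the worst treated area: "please rate the degree of discomfort you have had at areas that have been treated with your drug". Both arms complete it at Baseline and at Weeks 3, 6, 9, 12, 13, 14 and 16.

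**HyBryte, Weeks 3, 6 and 9 (6.2.3.2.1).** The SAEQ is in a first block, of which the text says "the following assessments will be conducted prior to light treatment". That block has no AE item. The second block opens with "Once the assessments are completed, the standard light treatment procedures will be conducted, as follows", and its first two items are the interval history and the documentation of AEs. Week 12 (6.2.3.3.1) has the same two blocks.

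**Valchlor, Weeks 3, 6 and 9 (6.2.4.1).** There is a single list, introduced by "At the clinic, the following assessments will take place before Valchlor is applied". Interval history and AEs are items 1 and 2, and the SAEQ is item 6. Week 12 (6.2.4.2) has the same order under "the following assessments and procedures will be completed before Valchlor is applied".

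**Follow-up, Weeks 13, 14 and 16 (6.2.3.4, 6.2.4.3).** Both arms have the same list, under "At each follow-up visit, the following will be conducted", with AEs ahead of the SAEQ.

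**What counts as an AE (9.1.1).** "This definition encompasses symptoms or signs reported by the subject", as well as findings detected by an observer. Section 9.4 does not say whether a mark on the SAEQ is to be entered as an AE, or whether an open question comes before the checklist.

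**The concern.** A patient who has just rated eight named skin symptoms is more likely to mention a mild one when asked about AEs, and the person recording AEs can see the completed form. Under the HyBryte text this holds at every on-treatment assessment visit. Under the Valchlor lists, if they are worked from top to bottom, that day's marks have not yet been made when AEs are taken.

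A preliminary comparison of safety is a stated objective (section 2), AEs are a listed safety variable (section 3), and results are tabulated by group (11.1). If the same skin experience is more likely to be entered as an AE in one arm, the AE tables partly reflect procedure. Within HyBryte, the change from SAEQ-first on treatment to AEs-first at follow-up also blurs a comparison of those two periods.

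The study is meant to expose practical issues for a larger comparative trial (sections 3 and 11.1), so an unequal AE procedure could be carried forward.

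**Working it through.** The plan states no figure on this point, so there is none to reproduce. The check sets the visit lists side by side and then counts enquiries.

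**Step 1: order at each visit type**

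| Visits | HyBryte | Valchlor |
|---|---|---|
| Weeks 3, 6, 9 | SAEQ, then AEs; sequence stated | AEs item 2, SAEQ item 6; sequence not stated |
| Week 12 | SAEQ, then AEs; sequence stated | AEs item 2, SAEQ item 6; sequence not stated |
| Weeks 13, 14, 16 | AEs listed before SAEQ; sequence not stated | same |

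The arms differ at Weeks 3, 6, 9 and 12. These are all the scheduled on-treatment AE enquiries that Valchlor patients have, and so the only matched on-treatment time points.

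**Step 2: how many enquiries are affected**

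- HyBryte: 24 light visits (4.1), each with AEs documented (6.2.3.1 to 6.2.3.3), plus 3 follow-up visits = 27. Counting the weekly marks in Table 2 instead gives 12 + 3 = 15.
- Valchlor: 4 assessment visits + 3 follow-up visits = 7.
- HyBryte enquiries with the SAEQ explicitly first: 4/27 = 15%, or 4/15 = 27% by weekly marks.
- Valchlor enquiries with the SAEQ explicitly first: 0 of 7. None has AEs explicitly first either; they are only listed first.

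**Step 3: earlier exposure to the checklist.** The SAEQ is completed at Baseline before randomization (6.2.2: "The SAEQ score will be collected and recorded"). Even if the list order is followed, a Valchlor patient has completed it 1, 2, 3 and 4 times by the AE enquiries at Weeks 3, 6, 9 and 12. HyBryte patients have the same earlier exposure plus the form just completed that day.

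**Step 4: the other skin check.** At every light visit, including the four matched ones, HyBryte patients have erythema, pain, pruritus, edema, hyperpigmentation, hypopigmentation, rash and vesiculation graded before and after light (7.2.1). By subject this overlaps six of the eight SAEQ items: rash, pain, swelling, redness, blistering and change in color. Valchlor has no counterpart.

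**Step 5: what a shift would do at this sample size.** The documents give no reporting rates, so every rate here is an assumption. Take 5 patients per arm (about 10 randomized 1:1, section 5.1) and no true difference. Let X_H ~ Bin(5, p_H) and X_V ~ Bin(5, p_V) be independent counts of patients with at least one recorded skin AE. Then P(X_H > X_V) is the sum over h > v of P(X_H = h) × P(X_V = v).

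| p_V | p_H | HyBryte higher | HyBryte lower |
|---|---|---|---|
| 0.30 | 0.30 | 36% | 36% |
| 0.30 | 0.35 | 43% | 30% |
| 0.30 | 0.40 | 50% | 25% |
| 0.20 | 0.40 | 64% | 14% |
| 0.30 | 0.60 | 75% | 9% |
| 0.40 | 0.80 | 86% | 4% |

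With equal rates from 0.2 to 0.6, each direction occurs in 34% to 38% of trials. The result runs from almost nothing to a strong tilt, depending only on the shift assumed. The table shows direction and sensitivity; it does not estimate the effect.

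**The case against.** The strongest case on the other side has five parts.

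- **The Valchlor order is inferred.** The only timing rule there is that everything precedes application of the gel, so a site could complete the SAEQ first and comply fully. This stands, and it rules out saying that Valchlor AEs are always taken before the marks exist. But one arm's order is then fixed and the other's left open, which is still not a common procedure.
- **Valchlor patients already know the checklist, and AE recording stays open.** Both are true. A symptom marked on the SAEQ in either arm can be recorded as an AE at that visit (9.1.1). A reader might infer that AE counts are prompted by a skin checklist in one arm only; the documents do not support that. What differs is same-visit prompting. Earlier exposure is shared by both arms, and a form with a 24-hour window completed at an earlier visit does not capture today's symptoms.
- **Larger asymmetries remain.** About 27 enquiries against 7, and the HyBryte-only grading, act in the same direction. Restricting the comparison to the four shared visits would remove the difference in scheduled enquiries being compared, but not the grading. This stands as a limit on what the fix achieves. It is no reason to leave the order unequal.
- **The size is assumed.** A reader might infer a 20-, 30- or 40-point difference from order alone by supposing that prompting doubles a rate of 0.2, 0.3 or 0.4. Those differences only restate the supposition, and they treat Valchlor patients as wholly unprompted.
- **The stakes are modest.** This is an open-label pilot of about 10 patients with descriptive tables and individual listings, and the SAEQ itself gives a comparison of skin symptoms with the same form at the same weeks. This stands and sets the severity.

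**Conclusion.** The concern holds in limited form. At the four matched on-treatment visits the HyBryte text requires the SAEQ before AEs are documented. The Valchlor lists place AEs ahead of the SAEQ without fixing an order. Same-visit prompting by a named skin checklist is thus written into one arm only, and AE ascertainment can differ between arms as a result.

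The expected direction is toward more mild skin AEs under HyBryte. This assumes that a named checklist raises reporting and that staff broadly follow the Valchlor list from top to bottom. The size cannot be derived from the documents. It is probably smaller than the effect of the unequal number of enquiries and the HyBryte-only grading; that ranking is a judgement, resting on the SAEQ-first order covering 4 of about 27 HyBryte enquiries. The documents do not demonstrate a bias of any stated size.

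This is a cheap improvement of minor severity.

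**What to change.** 1. In 6.2.3.2.1 and 6.2.3.3.1, move the interval-history and AE items ahead of the SAEQ, matching the order already listed in 6.2.4.1, 6.2.4.2 and both follow-up sections. Keep a line for recording AEs that arise after the light session.
2. In 9.4, state one sequence for both arms: an open AE question, then the SAEQ, then review of the marks under a common rule for when a mark becomes an AE. State that the sequence is binding, so that the Valchlor order no longer rests on list position.
3. Add a CRF source flag for events added from the SAEQ, and list AEs with and without them.

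The cost is a minor edit to the visit lists, a short addition to 9.4 and one CRF field, with no extra visit. The change does not equalise the number of AE enquiries or remove the HyBryte-only skin grading, so the study report should note both when AE counts are compared.
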